3.3. Secondary endpoints

The secondary objective is to evaluate whether based on the observations of the present study prediction of maxillary permanent canine impaction in young children is feasible.

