8.1. Sample size

Randomisation into expansion, extraction and control will be applied for patients without cross-bite having lack of space and – based on canine position and angulation - belonging to strata nCLB and nCLA. Within each of both strata, a randomisation will be performed using permuted blocks of varying size, yielding an equal number of patients in each of the three groups.

Success of the approach is defined as eruption without necessity of surgical intervention and integrity of the roots of the adjacent teeth. The primary endpoint is defined as the percentage success after 18 months. The trial is powered to show a difference between any of the pairs of groups. To have at least 80% power to show a higher success rate in one group compared to the other group, there are 78 subjects needed in each group assuming a success rate of 50% in the first group and 75% in the second group. The calculation is based on a two-sided χ^2 -test with alpha set at $0.05/3=0.0167$ to control the family-wise error rate at 5% (3 pairwise comparisons). However, to increase the amount of information for the development of a prediction model for success at 18 months (cfr. second aim of the study) it has been decided to increase the number of patients to 100 per group (300 patients in total).

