8.2. Analysis

The analysis of the primary endpoint will be based on a stratified χ^2 -test using a Bonferroni-Holm correction to correct for multiple testing (the strata are nCLB and nCLA). The same approach will be used for the comparison at the earlier timepoints (6 and 12 months). No interim analyses are planned, neither for efficacy, nor for futility. The analysis will be performed on an intent-to-treat basis.

A multivariable logistic regression model will be used to predict maxillary permanent canine impaction (=lack of success) on all included subjects. A backward selection procedure will be applied with 0.157 as critical level for the p-value. This critical value corresponds to the use of the Aikake Information Criterion (AIC) for model selection. With AIC we require that the increase in model χ^2 has to be larger than two times the degrees of freedom. This strategy provides a trade-off between erroneous inclusion and exclusion of covariates in a prediction model (Sauerbrei W. The use of resampling methods to simplify regression models in medical statistics. *Applied Statistics* 1999;48 (3):313–329.). The considered predictors are: strata formed by presence of cross-bite and parameters related to canine position and angulation, non-eruption, interceptive strategy, patient's age, stage of canine root formation, premature loss of deciduous teeth, familial history, space deficiency (arch length discrepancy).

As a sensitivity analysis, the prediction model will also be applied separately on the patients from the randomized and non-randomized part of the study.

9. Quality assurance

During this randomized clinical trial only standard operating procedures will be employed, such as i.e. removable expansion device, fixed expansion device, headgear, etc.. They are all validated, thoroughly described and widely used techniques. It will be up to the treating professional to decide for a given case which procedure to follow, in line with existing traditions in the specific collaborating centres. However, the main purpose should be attained which is expansion or in other words gaining extra space for tooth alignment. Depending on the interceptive treatment to be accomplished, decision will be taken to employ one specific treatment protocol to reach the goal set forward.

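### Section 8.2 selects the prediction model by backward elimination but plans no overfitting correction and no performance measure, so feasibility would be judged without an unbiased basis.

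*Combined protocol and SAP*

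**What the plan says.** Section 3.3 sets the secondary objective as judging whether "prediction of maxillary permanent canine impaction in young children is feasible". Section 8.1 and the synopsis give the prediction model as the reason for raising the randomised sample from 78 to 100 per group.

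Section 8.2 describes the model: a multivariable logistic regression for lack of success, fitted to everyone enrolled, randomised or not. On variable selection it says: "A backward selection procedure will be applied with 0.157 as critical level for the p-value". It justifies the level by its link to AIC and lists eight candidate predictors, several with more than two categories. It then adds: "As a sensitivity analysis, the prediction model will also be applied separately on the patients from the randomized and non-randomized part of the study".

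The description ends there. No section plans shrinkage, penalisation, bootstrap, cross-validation, a hold-out set or external validation. No section names a discrimination, calibration or accuracy measure, or says what result would count as feasible.

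**The concern.** When the same patients choose the predictors, estimate the coefficients and supply the fit, two things follow on average. The retained coefficients are too large, so high predicted risks are too high and low ones too low. Discrimination in those patients also looks better than it will be in the next child.

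A feasibility question is about performance in new patients. A list of retained covariates does not answer it, and an uncorrected AUC answers it with a bias in the favourable direction. This matters more than usual here because the model was the reason for randomising 300 − 3 × 78 = 66 patients beyond those needed for the primary comparison.

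**Working it through.** **1. The plan's own figures.** Section 8.1 is checked with p1 = 0.50, p2 = 0.75, two-sided alpha 0.05/3 = 0.0167 and power 80%:

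n = [z(1−α/2)·√(2·p̄·q̄) + z(0.80)·√(p1q1 + p2q2)]² / (p2 − p1)²

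= [2.394 × √0.46875 + 0.842 × √0.4375]² / 0.0625 = 77.1, so 78 per group. This agrees with the plan. The selection level also reproduces: P(χ² with 1 df > 2) = 0.157, the AIC level for a 1-df term.

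**2. Events and candidate parameters.**
- Failure is the model's event. The assumed success rates of 50% and 75% imply 25% to 50% failure, so 300 patients give 75 to 150 events (112.5 at the midpoint of 37.5%).
- The plan does not state the coding. A plain coding gives 5 df for the strata (cross-bite by A/B/C), 2 for strategy and about 1 for each of the other six items: 5 + 2 + 6 = 13. Assumed range: 10 to 20.
- Events per candidate parameter at 300 patients run from 75/20 = 3.8 to 150/10 = 15, and are 112.5/13 = 8.7 in the middle.
- Total N is not stated. The 300 are the randomised patients, so if recruitment is met the model's N is larger. Assumed range: 300 to 600.

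**3. Heuristic shrinkage.** Expected slope ≈ 1 − p/LR, where p is the number of candidate parameters, LR = −N·ln(1 − R²) and R² is on the Cox-Snell scale. At N = 300 and 37.5% failure, the largest possible Cox-Snell R² is 0.734.
- Nagelkerke R² 0.15: R² = 0.15 × 0.734 = 0.110, LR = 35.0. The slope is 0.71, 0.57 and 0.43 for 10, 15 and 20 parameters.
- Nagelkerke R² 0.30: R² = 0.220, LR = 74.6. The slope is 0.87, 0.80 and 0.73.

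**4. Simulation of the planned procedure.** Backward Wald elimination at p = 0.157; independent normal predictors, four of them truly predictive (log-odds 0.25 or 0.4 each); 37.5% failure; 300 replicates per scenario; evaluation in 20,000 new patients. Cells give the mean calibration slope, then apparent / new-patient AUC.

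| N | Candidates | True AUC about 0.64 | True AUC about 0.70 |
|---|---|---|---|
| 300 | 10 | 0.62; 0.659 / 0.599 | 0.81; 0.718 / 0.680 |
| 300 | 15 | 0.55; 0.667 / 0.597 | 0.73; 0.729 / 0.674 |
| 300 | 20 | 0.49; 0.676 / 0.590 | 0.67; 0.731 / 0.667 |
| 450 | 10 | 0.74; 0.649 / 0.611 | 0.88; 0.714 / 0.690 |
| 450 | 15 | 0.66; 0.659 / 0.609 | 0.83; 0.721 / 0.687 |
| 450 | 20 | 0.64; 0.668 / 0.611 | 0.80; 0.722 / 0.685 |
| 600 | 10 | 0.80; 0.647 / 0.618 | 0.90; 0.712 / 0.692 |
| 600 | 15 | 0.74; 0.654 / 0.616 | 0.87; 0.715 / 0.690 |
| 600 | 20 | 0.69; 0.660 / 0.614 | 0.83; 0.718 / 0.686 |

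The mean slope is below 1 in all 18 scenarios (0.49 to 0.90). The AUC excess runs from 0.712 − 0.692 = 0.020 to 0.676 − 0.590 = 0.086.

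**5. Stronger predictors.** With log-odds 0.6, 0.4, 0.4 and 0.3 (true AUC about 0.72), 40% failure and 13 candidates, the slope is 0.83, 0.87 and 0.93 at N = 300, 450 and 600. The AUC excess is 0.734 − 0.700 = 0.034, 0.731 − 0.706 = 0.025 and 0.727 − 0.714 = 0.013.

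**The case against.** The strongest reply is that the effect may be small. The model uses every enrolled patient, so 300 is a floor. A plain coding gives about 13 parameters, not 20. The protocol also stratifies on canine position because it expects position to be prognostic. With 600 patients and strong predictors the slope is 0.90 to 0.93 and the AUC excess 0.01 to 0.02. In some scenarios with 450 or 600 patients the 10–90% range of the slope passes 1 (0.76 to 1.06 at N = 600, 10 candidates, true AUC 0.70), so an individual fit may not be over-extreme at all. All of this stands, and it is why the size is given as a range and an average. It does not remove the point: without a corrected estimate, nobody reading the result could tell a mild case from a serious one.

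Some stronger readings are tempting but not supported:
- **The selection level is wrong.** It is pre-specified, fairly liberal and justified in section 8.2.
- **The sensitivity analysis is a failed validation.** The plan does not present it as validation, and comparing randomised with non-randomised patients is reasonable in itself. It simply does not measure performance in new patients.
- **The cited paper's title mentions resampling, so the plan contradicts its source.** Section 8.2 cites it for the trade-off in including and excluding covariates. A title is not evidence of a contradiction.
- **A worthless model would look useful.** With no true predictors, 300 patients and 20 candidates, apparent AUC is about 0.61 against a true 0.50. That illustrates the mechanism but does not size the problem in a trial whose strata are expected to be prognostic.

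**Conclusion.** The point holds as a gap in the analysis of a secondary objective. Carried out as written, section 8.2 gives risks that are too extreme on average and no unbiased basis for the feasibility judgement. For 300 to 600 patients, 10 to 20 candidate parameters and a true AUC of about 0.64 to 0.72, the mean calibration slope in new patients is about 0.5 to 0.9. The AUC is overstated by about 0.02 to 0.09, and by slightly less in the most favourable case. N, coding and predictive strength are all assumptions, because the documents do not give them. The simulations also use independent normal predictors, which the real ones will not be.

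A reader might infer that the feasibility question cannot be answered by this trial. The documents do not support that: the data needed for internal validation are the data already being collected, and the gap can be closed before analysis. The primary comparison is not affected.

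**What to change.** Add to section 8.2:
- The whole backward-selection procedure, starting from the full candidate list, is repeated in at least 500 bootstrap samples.
- The optimism-corrected c-statistic and calibration slope are reported beside the apparent values.
- The final coefficients are shrunk by the corrected slope.
- The feasibility statement rests on the corrected values, against a criterion that the sponsor writes down before analysis.

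Stating the coding of the eight candidates and the expected total N in the same place would let the likely overfitting be judged in advance. The selection level and the randomised/non-randomised sensitivity analysis can stay as they are.

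The cost is a short SAP addition, some analyst time and slightly less favourable reported performance. No new patients, visits or data are needed.

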4.1. Inclusion criteria

- General inclusion criteria:
 - Female or male patients coming to the department of Orthodontics of the UZ Leuven seeking for orthodontic advice.
 - Presenting with one or two non-fully erupted or impacted maxillary permanent canines (If bilateral impaction occurs, categorization into the different protocol groups will be based on the canine showing the worst position.)
 - Presenting with one or two maxillary permanent canines showing no more than $\frac{3}{4}$ root formation.
 - Any race
- In case of cyst around the area of the impacted canine, extraction of the persisting deciduous canine will be the treatment of choice. Also these cases will remain in follow up according to

our protocol but will not be randomized or attributed in one or other group. Specific canine related inclusion criteria for the allocation of patients in 3 different groups based on the presence of a cross bite (Group C), the absence of a cross bite with lack of space in the dental arch (Group nCL) and the absence of a cross bite with normal adequate space dimensions present in the dental arch (Group nCN):

- Group C (cross bite present)
 - Presence of a cross bite for all three subgroups: uni/bilateral/anterior cross bite. If end-to-end cross bite is present or tendency to cross bite, this will be considered as cross bite
 - Group CA: canine position sector ≤ 1 .
 - Group CB: canine position sector > 1 .
 - Group CC: canine position sector > 1 , canine angulation towards the midline $\geq 45^\circ$.
- Group nCL (no cross bite present)
 - Absence of cross bite and lack of space in the dental arch.
 - Group nCLA: canine position sector ≤ 1 .
 - Group nCLB: canine position sector > 1 .
 - Group nCLC: canine position sector > 1 , canine angulation towards the midline $\geq 45^\circ$.
- Group nCN (no cross bite present and normal space conditions in the dental arch)
 - Absence of cross bite and normal space conditions in the dental arch.
 - Group nCNA: canine position sector ≤ 1 .
 - Group nCNB: canine position sector > 1 .
 - Group nCNC: canine position sector > 1 , canine angulation towards the midline $\geq 45^\circ$.

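### The prediction model in Section 8.2 has no term for one versus two study canines; if either canine's failure counts against the child, predicted risk can be too low for two-canine and too high for one-canine children

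*Combined protocol and SAP*

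**What the plan says.** Section 4.1 describes eligible children as "Presenting with one or two non-fully erupted or impacted maxillary permanent canines", and adds: "If bilateral impaction occurs, categorization into the different protocol groups will be based on the canine showing the worst position". That rule cannot be applied without assessing both canines, so the number must be known for every child before group assignment.

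Section 8.2 plans a multivariable logistic regression to "predict maxillary permanent canine impaction (=lack of success) on all included subjects". Subjects are the unit named, which implies one outcome per child. The candidates open with "The considered predictors are: strata formed by presence of cross-bite and parameters related to canine position and angulation, non-eruption, interceptive strategy" and continue with "patient's age, stage of canine root formation, premature loss of deciduous teeth, familial history, space deficiency (arch length discrepancy"). Neither the number of canines nor laterality is named. Non-eruption is listed without a definition, and nothing says that it counts canines. On selection: "A backward selection procedure will be applied with 0.157 as critical level for the p-value". As a sensitivity analysis, the model is also to be applied separately to the randomised and non-randomised parts.

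The outcome rests on Section 8.1: "Success of the approach is defined as eruption without necessity of surgical intervention and integrity of the roots of the adjacent teeth". Neither this definition nor the one in Section 3.1 says whether a child with two study canines must meet it for both.

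**The concern.** Prediction is the second stated aim, and Section 8.1 raises the sample from 78 to 100 per group to support it. A child with two study canines may have two chances to need surgery and two sets of adjacent roots at risk. The model cannot see this:

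- The position stratum does not stand in for the count. Under the worst-canine rule, a one-canine and a two-canine child with the same worst canine carry the same label.
- Backward selection can drop listed candidates but cannot add an unlisted one.
- The sensitivity analysis applies the same model to two subsets, so it would not show the gap.

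At stake is how well predicted risk agrees with observed risk in each of two groups that can be told apart at entry. Adding the term after seeing the data would be an unplanned choice; adding it now is not.

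**Working it through.** **1. The plan's own figure.** Inputs from Section 8.1: success 50% and 75%, two-sided alpha 0.05/3, power 80%. With pooled variance and no continuity correction, n = [2.394·√(2·0.625·0.375) + 0.842·√(0.25 + 0.1875)]² / 0.25² ≈ 77.1, so 78 per group. This reproduces the plan. Nothing in the present point changes it.

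**2. Set-up.** No figure in the documents measures the effect of the omission, so what follows is illustration. Let q be the failure risk per canine, ρ the within-child correlation and w the share of two-canine children. Neither ρ nor w is given in the documents. If either canine's failure makes the child a failure:

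- one-canine risk = q
- two-canine risk = 1 − [(1−q)² + ρ·q·(1−q)]
- d = two-canine risk − one-canine risk
- a model without the count predicts q + w·d for both, which is w·d too high for one-canine children and (1−w)·d too low for two-canine children.

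**3. Equal risk for both canines, q = 40% (assumed).** Errors in percentage points, one-canine / two-canine:

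| ρ | two-canine risk | d | w = 20% | w = 30% | w = 40% |
|---|---|---|---|---|---|
| 0 | 64.0% | 24.0 | +4.8 / −19.2 | +7.2 / −16.8 | +9.6 / −14.4 |
| 0.3 | 56.8% | 16.8 | +3.4 / −13.4 | +5.0 / −11.8 | +6.7 / −10.1 |
| 0.6 | 49.6% | 9.6 | +1.9 / −7.7 | +2.9 / −6.7 | +3.8 / −5.8 |

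That is 2 to 10 points too high and 6 to 19 too low.

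**4. A better-placed second canine.** Grouping is by the worse canine, so the other is no worse placed. Assume 40% and 10%, independent. Two-canine risk = 1 − 0.60·0.90 = 46%, so d = 6 points. At w = 20% the errors are +1.2 / −4.8; at w = 40% they are +2.4 / −3.6. Positive correlation would shrink them further. Steps 3 and 4 together span about 4 to 19 points too low and 1 to 10 too high.

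**5. Failure rates implied by Section 8.1.** The plan is powered "assuming a success rate of 50% in the first group and 75% in the second group", which gives failure rates of 50% and 25%. I used equal canines, ρ from 0 to 0.8 and w of 20% or 40%.

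- Largest errors: q = 50%, ρ = 0 gives a two-canine risk of 75%. At w = 20% the model gives 55%, which is 20 points too low for two-canine children. At w = 40% it gives 60%, which is 10 too high for one-canine children.
- Smallest errors: q = 25%, ρ = 0.8 gives 1 − (0.5625 + 0.8·0.1875) = 28.75%. At w = 40% the model gives 26.5%, about 2 points too low. At w = 20% it gives 25.75%, about 1 too high.

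This wider grid therefore runs from 2 to 20 points too low and 1 to 10 too high.

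**6. Does the stratum absorb it?** I simulated 400,000 children with w = 30%, each canine independently in the worse position with probability one half, a shared child effect, and a logistic model containing the worst-canine stratum but not the count.

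| Scoring | Children | Observed failure | Predicted |
|---|---|---|---|
| Either canine fails | two canines | 58.4% | 49.6% |
| Either canine fails | one canine | 40.7% | 44.5% |
| Worst canine only | two canines | 45.5% | 45.4% |
| Worst canine only | one canine | 40.6% | 40.7% |

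Under either-canine scoring the stratum does not remove the error. Under worst-canine scoring there is none to remove.

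**7. The other zero case.** With ρ = 1 and equal risks, two-canine risk = 1 − [(1−q)² + q(1−q)] = q, so d = 0.

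**8. If the count is uninformative.** At a critical level of 0.157, a one-degree-of-freedom noise term stays in the model in about 16% of samples.

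**The case against.** The strongest reply is that the harm depends on a scoring rule the documents do not contain. The only rule for bilateral cases assigns the group by the worst canine; if the outcome follows the same canine, the error vanishes. This stands, and it is why the conclusion is conditional. The synopsis gives the endpoint in the plural, as eruption of canines, but that may be generic wording and settles nothing. The missing rule is the upstream gap, and a one/two term is hard to interpret until it is filled.

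Second, the equal-risk illustrations lean upward, because the second canine may be clearly better placed. This also stands; step 4 brings the error down to 4-5 and 1-2 points.

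Third, the count needs a definition. Section 4.1 covers canines not yet fully erupted as well as impacted ones, and on the broadest reading many children could count as two, leaving the term little to add. This stands and is taken into the fix.

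Fourth, a model without a covariate returns risk averaged over it, which is less refined but not invalid. Sex and centre are absent too, and choosing candidates is largely the investigators' judgement. This is fair: the documents do not show that the count is prognostic. What remains is that the count is already needed for grouping, bears directly on how often a child can fail under one natural reading, and costs little to include.

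A reader might also infer that adding the term is free because selection would discard it if useless. The plan's critical level does not guarantee that, as step 8 shows.

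**Conclusion.** The omission is a fact of the text: the count is known at entry, is not a candidate, and cannot be recovered by the stratum, the selection step or the sensitivity analysis. The consequence is conditional. If either canine's failure makes the child a failure, predicted risk can be about 4 to 19 points too low for two-canine children and 1 to 10 too high for one-canine children. This assumes 40% failure for the worse canine, a 20-40% two-canine share and, with equal canines, a correlation of 0 to 0.6. The wider grid in step 5 moves the two-canine range to 2 to 20 points. The error is about zero if only the worst canine is scored or both canines always share an outcome.

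A reader might infer that the predictions will be wrong in both groups, or that the trial's main result is compromised. The documents support neither. They give no child-level rule for two canines, no share of two-canine children and no within-child correlation. The sample size and the primary comparison do not use this model. This is a cheap improvement to a secondary model, held with low confidence as to its size.

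**What to change.** In Section 8.2:

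- Add the number of study canines at inclusion (one or two) to the considered predictors, under the same backward selection.
- Define the count from the entry radiograph, for example canines in sector > 1, or all canines not fully erupted that meet Section 4.1. Choose one definition before analysis.
- Offer the same term in the models for the randomised and non-randomised parts.

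In Section 8.1 or 8.2, state how success is scored for a child with two study canines. Without that rule the coefficient has no clear meaning.

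Cost: one extra degree of freedom in a secondary model, about a 16% chance of keeping the term if it carries no information, and no new data collection. The added term leaves the primary comparison and the sample size as they are.

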3.4. Trial Design

The present trial is a non-commercial prospective randomized controlled trial of patients presenting with permanent maxillary canine impaction. These patients are selected at the intake consultation of the department of Orthodontics, UZ Leuven. A panoramic radiograph is the standard radiographic examination procedure at this particular moment in time for visualization of dental development and associated pathology. Maxillary permanent canine impaction may be diagnosed based on this radiograph by analysing predefined parameters correlated with maxillary permanent canine impaction. In case of signs of mild to severe canine impaction, an additional standard long cone apical radiograph (LCAR) is taken radial to the dental arch at the estimated normal permanent canine position to detect possible root resorption of the adjacent lateral incisor and to document the vertical permanent canine position. A CBCT will only be taken in the following two cases: evidence of damage to the adjacent teeth and for the purposes of canine exposure surgery. Specific inclusion and exclusion criteria are described in paragraph 4.

Patients are stratified based on the presence of a cross bite (Group C) versus no cross bite (Group nC), either a frontal or a uni-/bilateral cross bite. Further categorization is performed for both groups C and nC into 3 subgroups, A, B and C, depending on the obtained parameters related to canine position and angulation. Subgroup CA contains the rather normally positioned canines, indicative for rather normal maxillary permanent canine eruption. This group will function as the control group within Group C. Badly positioned canines will be categorized into subgroup CB constituting the study group. Finally subgroup CC includes those canines that are extremely badly positioned (see paragraph 4) requiring specific additional action.

Cross bite group.

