7.3. Treatment stopping rules

Treatment or follow up will immediately stop when compliance of the patient becomes a problem or when for one or other reason, the patient or his/her parents/guardians want to discontinue follow up/treatment:

- The patient does not comply with treatment (does not follow the given instructions, misses the appointments).
- The patient's poor levels of oral hygiene compromise the health of the teeth and/or surrounding soft tissues.
- The patient wishes to stop treatment.

8. Statistics

Measures taken to minimize bias:

- Allocation concealment: randomization of the treatment options by a randomization list.
- Blinding measures: measurements of canine inclination on OPG will be taken by two operators, blinded to each other's measurements as well as to the name of the patient, treatment followed or occlusion details.
- Previous power calculation

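### Read naturally, section 8.2 gives the prediction model canine position and angulation only as allocation strata, leaving the randomised patients one binary sector term and no angulation term

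*Combined protocol and SAP*

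**What the plan says.** Section 8.2 plans a multivariable logistic model for lack of success, fitted to every included patient, with backward selection at p = 0.157. The same model is to be applied separately to the randomised and the non-randomised patients as a sensitivity analysis.

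The first candidate predictor is "strata formed by presence of cross-bite and parameters related to canine position and angulation". The others are "non-eruption, interceptive strategy, patient's age, stage of canine root formation, premature loss of deciduous teeth, familial history, space deficiency (arch length discrepancy". Canine sector and canine angle have no entry of their own.

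Section 3.4 describes "3 subgroups, A, B and C, depending on the obtained parameters related to canine position and angulation". Section 4.1 gives the cut-points. For the group with no cross bite and lack of space they are:
- The first randomised stratum is written as "Group nCLA: canine position sector ≤ 1", with nothing on angle.
- The second randomised stratum is written as "Group nCLB: canine position sector > 1", again with nothing on angle.
- The third category, which is not randomised, is written as "Group nCLC: canine position sector > 1 , canine angulation towards the midline"; its threshold is 45° or more.

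Groups C and nCN use the same cuts. Section 8.1 randomises only nCLA and nCLB and calls them strata. It raises the trial from 78 to 100 per group "to increase the amount of information for the development of a prediction model for success at 18 months". The bias measures that open section 8 state that "measurements of canine inclination on OPG will be taken by two operators", blinded to each other and to treatment.

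**The concern.** Prediction is the trial's secondary objective, and the prediction model is the only reason section 8.1 gives for the additional patients. The two radiographic features that define how badly a canine is placed nevertheless seem to reach that model only after being cut into categories. The cuts serve to decide who is randomised and who is managed in another way; the documents do not present them as cuts chosen for prediction.

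Backward selection cannot recover a predictor that was never offered to it. If angulation below 45°, or sector beyond the first cut, carries risk information, the planned model cannot use it. The randomised patients are also where angulation could best be separated from treatment, because treatment there does not depend on it.

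**Working it through.** **1. The plan's own figure.** Inputs from section 8.1: success 50% against 75%, two-sided α = 0.05/3 (z = 2.394), power 80% (z = 0.842), mean proportion 0.625.

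n = [2.394·√(2·0.625·0.375) + 0.842·√(0.5·0.5 + 0.75·0.25)]² / 0.25² = [1.639 + 0.557]² / 0.0625 ≈ 77.1, rounded up to 78 per group.

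The figure reproduces (no continuity correction). Power is 80.5% at 78 per group and about 90% at 100. The enlargement is 300 − 3·78 = 66 patients, and 100/78 = 1.28, so it adds 28% to the randomised sample. Put the other way, coding that keeps less than 234/300 = 78% of the information would cancel it.

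**2. What terms the strata provide.** From section 4.1:

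| Category | Sector | Angulation | Randomised (nCL) |
|---|---|---|---|
| A | ≤ 1 | no criterion | yes |
| B | > 1 | no criterion | yes |
| C | > 1 | ≥ 45° | no |

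- Randomised patients: A against B, which is 1 degree of freedom for sector and 0 for angulation.
- Full model: angulation appears only as C against B, within sector > 1. Section 3.4 changes treatment at that boundary: CC adds extraction to the expansion that CA and CB receive; nCLC receives expansion followed by extraction; nCNC receives extraction where nCNA and nCNB receive none. The contrast therefore largely coincides with interceptive strategy, itself a candidate predictor. It is not wholly collinear, because extraction depends on the deciduous tooth still being present.
- As written, B has no upper angulation limit, so a sector > 1 canine at ≥ 45° fits both B and C. The definitions must be reconciled, but on either reading A against B holds no angulation criterion.

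**3. Information kept by the sector cut.** The documents give no distribution. Assume sectors 1 to 4 with shares 50/25/15/10%.
- Mean = 0.50·1 + 0.25·2 + 0.15·3 + 0.10·4 = 1.85
- Variance = (0.50 + 1.00 + 1.35 + 1.60) − 1.85² = 1.0275
- Covariance with the indicator of sector > 1 = 1.35 − 1.85·0.5 = 0.425
- Squared correlation = 0.425² / (1.0275·0.25) = 0.70

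Under these shares 300 patients inform a linear sector effect about as well as 0.703·300 ≈ 211 would. Angulation is not cut in these patients; it is left out.

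**4. Model level, first illustration.** 300 randomised patients, 400 replicates, test samples of 4,000. Assumed: the shares above; angle mean 18 + 5·(sector − 1) degrees, SD 9, below 45°; log-odds linear in both.

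| Gradient | Chi-square, strata | Chi-square, measured | Gain | Kept by strata | c-statistic in new data, strata / measured |
|---|---|---|---|---|---|
| weak | 27.4 | 33.5 | +22% | 82% | 0.656 / 0.674 |
| moderate | 34.1 | 49.0 | +44% | 70% | 0.671 / 0.715 |
| strong | 41.2 | 68.6 | +67% | 60% | 0.692 / 0.757 |

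**5. Model level, second illustration.** Assumed: five sector levels, angle mean 20° and SD 12°, latent correlation 0.4, 37% failure, odds ratio 1.3 to 1.7 per sector and 1.0 to 2.0 per 10°. The A/B term keeps 75% of the chi-square when angle has no effect (19.1 of 25.6 per 300 patients at odds ratio 1.7 per sector). It keeps 27% when angle is strong and sector weak (13.4 of 50.3).

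**The case against.** **The sentence can be parsed differently.** It could list two items: strata by cross bite, and the position and angulation parameters themselves. Section 3.4 gives this some support, since it stratifies on cross bite and derives A/B/C from the obtained parameters. The reading is possible but less natural. Sections 8.1 and 8.2 both use strata for nCLA and nCLB, and space, which also defines subgroups, gets its own entry as arch length discrepancy while sector and angle do not. Even on this parse, 8.2 names neither the parameters nor their coding.

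**The main model does contain angulation.** This stands. A reader might infer that angulation is missing altogether, but the C categories carry a 45° cut. It is absent from the randomised patients and from the separate fit on them.

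**The size can be overstated.** A reader might infer that the coding gives away more than the 66 extra patients add. The documents do not support that: in the weak case above the gain is 22%, below the 28% from enlargement. Nor do the textbook figures for a normal predictor cut in two (64% kept at the median, 49% at 20/80) apply, because sector is ordinal and angulation is omitted. Both illustrations also generate risk linear in sector and angle and then fit that form, which favours measured values.

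**Patients in one category do not all get the same predicted risk.** Correct: age, root formation, space and the other predictors still separate them.

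**The strata are design variables.** A/B is the randomisation stratum, and category determines treatment outside the randomised part. That is a fair reason not to insist on removing them.

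**The blinded readings may not be baseline readings.** Section 8 gives neither unit nor time point, so duplicate baseline readings in degrees cannot be assumed. Some baseline angulation must exist, however, because the 45° criterion needs it.

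**Conclusion.** The point holds as a weakness of the secondary prediction analysis, on the natural reading of section 8.2. The term count for the randomised patients follows from the stratum definitions and needs no assumption.

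The size of the loss does rest on assumptions, because the documents give no distributions or effects. In the two illustrations the strata keep between 27% and 82% of the chi-square reached with measured values, on either side of the 78% at which the enlargement is cancelled. The supportable statement is that the coding can lose a material part of what the enlargement was meant to supply, not that it must lose all of it. If sector and angle have little bearing on success, the loss is small.

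The stratified primary test, the 78 per group and the randomisation are unaffected. This is worth correcting because it is cheap, but it does not threaten the trial's main conclusion.

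**What to change.** In section 8.2, name these candidate predictors explicitly:
- cross bite, yes or no;
- canine sector as recorded, entered as an ordinal score;
- the baseline canine angulation used for allocation, continuous, linear or with one spline term.

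In bilateral cases use the worse canine, which section 4.1 already makes the basis for categorisation. Offer these in addition to, or in place of, the A/B/C category, and fix the coding before outcomes are seen. If measured values were always intended, one sentence saying so is enough.

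**Cost.** A sentence or two of text. Sector and a baseline angulation are already needed to allocate patients; the plan should state which film and which reading supply the angle. There is a linearity assumption to check. Replacing the strata uses 3 to 4 degrees of freedom, against 2·3 − 1 = 5 for cross bite by A/B/C. Keeping them adds 2 to 3 (1 for sector, 1 to 2 for angle). With failure between 25% and 50%, 300 patients give 75 to 150 failures, so the addition is modest.
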